10.6 Data Pooling

Data will be pooled from multiple study sites for this analysis, the basis for pooling comes from three factors:

- The study sites must implement one common protocol.
- The CRO must closely monitor study site protocol compliance.
- The study sites must use common data collection procedures.

10.7 Primary Statistical Analysis

T3 Group: The mean myopic progression after cessation of MiSight wear will be compared to the mean annual progression for the first three years (MIST-401 Part 1) for this same group of subjects ("T3 Baseline") on a pairwise basis using linear mixed models. The model will include part, site, and the interaction of site-by-part as fixed effects and subject (nested in site) and eye as random effects. The fixed covariates: subject age group, sex, ethnicity, and baseline myopia (refractive error or axial length) may also be included. If there are convergence issues with the model some or all the covariates may be removed as required.

Statistical non-inferiority will be concluded if the 95% confidence limit of the mean difference of the progression rate after cessation compared to the T3 Baseline rate is greater than -0.25D/year for spherical equivalent refractive error or less than +0.1mm/year for axial length.

T6 Group: The mean myopic progression after cessation of MiSight wear will also be compared to the T3 Baseline mean annual progression using a linear mixed model. The model will include group (T6 or T3), site, and the interaction of site-by-group as fixed effects and subject (nested in site) and eye as random effects. The fixed covariates: subject age group, sex, ethnicity, and baseline myopia (refractive error or axial length) may also be included. If there are convergence issues with the model, some or all the covariates may be removed as required.

Statistical non-inferiority will be concluded if the 95% confidence limit of the mean difference of the progression rate after cessation compared to the T3 Baseline rate is greater than -0.25D/year for spherical equivalent refractive error or less than +0.1mm/year for axial length.

10.8 Secondary Statistical Analysis

The myopic progression after cessation of MiSight wear will be compared to the mean annual myopic progression for previous 3 year's MiSight treatment (MIST-401 – Part 2) on a pairwise basis using linear mixed models. The model will include treatment, site, years of MiSight wear (T6 or T3), and the interaction of site-by-treatment as fixed effects and subject (nested in site) and eye as random effects. The fixed covariates: subject age group, sex, ethnicity, and baseline myopia (refractive error or axial length) may also be included. If there are convergence issues with the model some or all the covariates may be removed as required.

A statistical difference will be concluded if the 95% confidence limit of the mean (test-control) difference is greater than 0 for spherical equivalent refractive error or less than 0 for axial length.

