3.2 Study Rationale

Since there is no defined level of myopia progression that would constitute a classification of 'acceleration' or 'rebound', the primary and secondary hypotheses are targeted primarily on quantifying any change in myopia progression rate (SERE and AL) in these post treatment groups.

The primary outcome analysis will compare the rate of myopia progression after cessation of MiSight wear to the average rate of myopia progression found in the Control group (Proclear 1-Day) in the 3-year MIST-401 - Part 1 study. The myopia progression rate should not be more than this progression rate found with standard contact lens usage.

The secondary outcome analysis will compare a subject's rate of myopia progression after cessation of MiSight wear to their average rate of myopia progression with MiSight lenses for the immediately previous three years in the MIST-401-Part 2 study. Because MiSight lenses have demonstrated a myopia control effect, we might expect a slightly increased rate of myopia progression when wearing regular lenses.

3.3 Primary Outcome Hypothesis

- i. The mean myopic progression (Δ SERE) after cessation of MiSight wear will be noninferior to (i.e. not greater than) the mean annual myopic progression of the Control group in MIST-401-Part 1.
- ii. The mean myopic progression (Δ AL) after cessation of MiSight wear will be noninferior to (i.e. not greater than) the mean annual myopic progression of the Control group in MIST-401-(Part 1).

A non-inferiority margin of 0.25D or 0.1mm will be used for SERE and AL respectively.

3.4 Secondary Outcome Hypotheses

- i. The mean myopic progression (Δ SERE) after cessation of MiSight wear will be greater than the mean annual myopic progression for the immediately previous 3 year's MiSight treatment (MIST-401-Part 2).
- ii. The mean myopic progression (Δ AL) after cessation of MiSight wear will be greater than the mean annual myopic progression for the immediately previous 3 year's MiSight treatment (MIST-401-Part 2).

3.5 Tertiary Outcome Hypotheses

3.6 Safety Hypothesis

The study lenses are approved in all the countries where the study is taking place, therefore, no safety end points are required.

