10 SAMPLE SIZE AND STATISTICAL METHODS

10.1 Sample Size Rationale

All eligible subjects that complete the MIST-401 Part 2 study will be invited to continue in this study. No new subjects will be enrolled. Based on the current study, there will be approximately 90 subjects completing the study: 44 with six years of MiSight experience (Group T6; original test group in Part 1) and 46 with three years of MiSight experience (Group T3; original control group in Part 1).

Primary Hypothesis

From the MIST-401 Part 1 study, the standard deviations for the paired mean difference and the 2-sample means were estimated. From these the sample sizes of 44 in group T6 and 46 in group T3 will provide at least 99% power to detect non-inferiority.

	Spherical Equivalent Refractive Error (D)		Axial Length (mm)	
	T3:	T6:	T3:	T6:
Hypothesis	Mean progression after 1-year cessation vs. "T3 Baseline" (Control group mean progression Y1-3)			
Test	Non-inferiority Paired (H₀: δ ≤ NIM)	Non-inferiority 2-sample (H₀: δ ≤ NIM)	Non-inferiority Paired (H₀: δ ≤ NIM)	Non-inferiority 2-sample (H₀: δ ≤ NIM)
Alpha	5% (1-sided)	5% (1-sided)	5% (1-sided)	5% (1-sided)
Sample Size	46	44	46	44
Expected Mean Difference	0.00D	0.00D	0.0 mm	0.0 mm
SD of mean or mean difference (σ)	0.36D	0.20D	0.10 mm	0.10 mm
Non-inferiority Margin (NIM)	0.25D	0.25D	0.1mm	0.1mm
Power	100%	100%	100%	99%

N.B. Calculations performed using Hintze, J. (2013). PASS 12. NCSS, LLC. Kaysville, Utah, USA. www.ncss.com.

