10.3 Statistical Considerations

All statistical analyses will be performed using the SAS software Version 9.4 or later (SAS Institute, Cary, NC). All data summaries will be performed using Microsoft Excel 2013 or later.

The final analysis will be completed after all subjects have been exited from the study, all queries have been resolved, and the database has been locked.

The mean annual myopic progression will be calculated by dividing the myopic progression for the years in question by the number of years for each subject.

The overall type I error rate will be preserved at 5%. The co-primary hypotheses will be simultaneously evaluated using α =0.05.

Data from unscheduled visits will not be included in the analysis.

10.4 Analysis Population

The statistical analysis for efficacy hypothesis testing will be performed as follows:

- 1. All available data this will include all data from subjects that have completed followup visits. Counts of missing data will be included in the summary statistics.
- 2. Intent-to-treat this will include any subject that has completed at least the 6-month visit. Missing data for 12-month myopia progression and axial length will be extrapolated, where possible, from the 6-month data for the intent-to-treat analysis.

10.5 Descriptive Statistics

Descriptive statistics will be reported at dispensing and each follow-up visit. Continuous variables will be summarized using mean, standard deviation, and range; and categorical data variables will be summarized using percent frequency distribution, mean, and SD. Nominal variables will be summarized using percentages.

Summaries will be presented by group (T3: 3 years of MiSight wear and T6: 6 years of MiSight wear.

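### The T3 primary model (10.7) and the secondary model (10.8) omit a subject-by-period random effect and do not define the eye effect; if eye is nested in subject, the confidence limits are too narrow

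*Combined protocol and SAP*

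**What the plan says.** For group T3, section 10.7 compares progression after cessation with the same subjects' mean annual progression in MIST-401 Part 1. It calls the comparison pairwise and uses a linear mixed model: "The model will include part, site, and the interaction of site-by-part as fixed effects and subject (nested in site) and eye as random effects". Covariates are optional; among them, "baseline myopia (refractive error or axial length) may also be included". The decision rule begins "Statistical non-inferiority will be concluded if the 95% confidence limit of the mean difference" and compares that limit with -0.25 D/year (SERE) or +0.1 mm/year (axial length).

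Section 10.8 is a second within-subject comparison, cessation against Part 2. Its model ends with "the interaction of site-by-treatment as fixed effects and subject (nested in site) and eye as random effects". Its rule is: "A statistical difference will be concluded if the 95% confidence limit of the mean (test-control) difference is greater than 0" for SERE, with the opposite sign for axial length. The matching hypothesis in 3.4 is that progression "after cessation of MiSight wear will be greater than the mean annual myopic progression for the immediately previous" three years on MiSight.

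On error control, section 10.3 states: "The overall type I error rate will be preserved at 5" per cent. It names the co-primary hypotheses and sets no alpha for 10.8. The sample-size table in 10.1 gives each primary test a one-sided 5% alpha. For T3 it gives n = 46 and SDs of 0.36 D and 0.10 mm, without saying whether these are per subject or per eye.

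Both eyes are measured (10.2, Appendix A). Nothing in the plan averages the eyes, selects a study eye, or specifies a repeated-measures covariance or a robust variance.

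**The concern.** Each subject supplies four values: two eyes in each of two periods. The quantity tested is the change from one period to the other. Anything constant within a subject, or within an eye nested in a subject, drops out of that change. What remains is the subject's own change, largely shared by both eyes if they progress together, plus eye-specific noise. The shared part needs a subject-by-period random effect. Without one it goes into the residual, and the two eyes count as nearly independent pairs.

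The wording leaves a second gap. Subject is nested in site, but eye is given no nesting. A statistician could code it as nested in subject or as a right/left factor common to all subjects. The two codings give different standard errors, and neither is right in general.

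At stake are the T3 interval, the 5% error rate promised in 10.3, and the 10.8 test. The 10.8 test is made against zero with no margin as a buffer, so the limit itself decides the conclusion. The T6 primary model is not affected: each subject enters it in one period only, so the subject effect already carries the correlation between eyes.

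**Working it through.** **Inputs from the plan (10.1, 10.7).** T3 n = 46; T3 and T6 together 90; SD 0.36 D and 0.10 mm; margins 0.25 D and 0.1 mm; expected difference 0; one-sided 5%; four sites.

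**Assumptions, not in the documents.** rho, the between-eye correlation of the period-to-period change, 0.5 to 0.9. k, the stable between-eye variance divided by the subject-by-period variance, 0 to 4. The SDs are read as subject-level. Sites are taken as equal in size.

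**The plan's own figures.** Noncentral-t power at one-sided 5% is 99.9% (T3 SERE), above 99.9% (T6 SERE), above 99.9% (T3 axial length) and 99.9% (T6 axial length). The plan states 100%, 100%, 100% and 99%, so its power reproduces.

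**Variance algebra.** Let sp, eye and res be the subject-by-period, stable eye-in-subject and residual variances. Then rho = sp/(sp + res) and k = eye/sp.

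- True variance of the period contrast: (2sp + res)/n.
- Eye nested: the model uses about (sp + res)/n. The SE is too small by sqrt[(2sp + res)/(sp + res)] = sqrt(1 + rho) = 1.22, 1.34, 1.38 at rho 0.5, 0.8, 0.9. With four sites the residual pools 42 df carrying 2sp + res and 46 df carrying res. At rho 0.8 (sp = 0.8, res = 0.2) that is 0.2 + (84/88)(0.8) = 0.964, and sqrt(1.8/0.964) = 1.37. The three factors become 1.24, 1.37 and 1.41.
- Eye nested, small k: the eye variance estimate has expectation about eye - sp/2, so it tends to zero when k < 0.5. The residual then pools to res + (2/3)(eye + sp). At k = 0 and rho 0.9 the factor is sqrt[1.9/(0.1 + 0.6)] = 1.65 (1.69 with four-site df).
- Eye crossed: the model uses about [res + (2/3)(eye + sp)]/n. This equals the true value only if eye = 2sp, that is k = 2. Below that it is too small, above it too large.

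**Simulated error rates, T3, true difference at the margin** (40,000 replicates per cell, rho 0.5 / 0.8 / 0.9):

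| Eye effect | k | Nominal 5% | Nominal 2.5% |
|---|---|---|---|
| Nested | 0 | 11.0 / 15.4 / 16.6% | 7.3 / 11.2 / 12.5% |
| Nested | 0.25 | 10.2 / 12.9 / 14.1% | 6.5 / 8.8 / 10.1% |
| Nested | 1 to 4 | 8.9-9.4 / 11.1-11.5 / 12.1-12.6% | 5.4-5.9 / 7.2-7.6 / 8.2-8.8% |
| Crossed | 1 | 7.4 / 8.4 / 8.8% | 4 to 5.5% |
| Crossed | 2 | 5.0 to 5.2% | not tabulated |
| Crossed | 4 | 2.4 / 1.9 / 2.0% | under 1% |
| Subject-by-part added | all | 4.7 to 5.3% | 2.3 to 2.6% |

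The 2.5% column applies if the 95% limit comes from a two-sided interval. At rho 0.3 with eye nested, 5% becomes 7.5 to 9%. At rho 0 with eye nested there is no problem.

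**Section 10.8, n = 90, one tail** (the same in either direction). Nested, k = 1 to 4: 2.5% becomes 5.3 to 8.1% and 5% becomes 8.7 to 12.2%. Nested, k = 0: 7.2 to 12.1% and 11.1 to 16.2%. Crossed, nominal 2.5%: 4.1 to 5.3% at k = 1, nominal at k = 2, 0.6 to 0.9% at k = 4.

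**Direct REML fits** (30 per setting, rho 0.8, SD 0.36 D; true SE 0.36/sqrt(46) = 0.053 D). Mean SE at k = 0.25 / 1 / 4: nested 0.037 / 0.038 / 0.038; crossed 0.037 / 0.043 / 0.067; with subject-by-part 0.054 / 0.052 / 0.052.

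**When the T3 verdict would change (eye nested).** With the correct SE, non-inferiority fails once the estimated excess passes 0.25 - 1.682 x 0.0531 = 0.161 D. With the nested SE (0.0531/1.24 to 0.0531/1.41) it fails only past 0.179 to 0.187 D (0.198 D at k = 0). For axial length the figures are 0.075 mm against 0.080 to 0.083 mm (0.086 mm). With a two-sided 95% interval the SERE figures are 0.143 D against 0.165 to 0.175 D (0.188 D). If the true excess is 0.00 D, an estimate past 0.161 D lies 0.161/0.0531 = 3.0 SEs out, a probability of about 0.1% (about 0.4% past 0.143 D).

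**The case against.** The strongest objection concerns direction. The text marks nesting for subject and not for eye, so read literally eye is crossed, and the limits could then be too narrow, right or too wide. That stands: the too-narrow conclusion is conditional on nesting. It does not rescue the specification, because the crossed form is right only near k = 2 and the text does not settle which form applies.

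Second, the primary verdict is almost never affected at the planned difference of zero. That also stands. The exposed test, 10.8, is secondary, has no stated alpha, SD or power, and so its effect can be given only as an error rate.

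Third, if the 95% limit is two-sided, the nominal rate is 2.5%, and the T3 rate at rho 0.5 (nested, k of 1 or more) is 5.4 to 5.9%, barely above the 5% in 10.3. This is fair, but at rho 0.8 to 0.9 it is 7 to 9%, and 10.1 supports the one-sided 5% reading.

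Fourth, a subject-level paired analysis may have been intended: 10.1 plans a paired test with n = 46, and 10.3 computes annual progression per subject. That suggests the intent, but the sentence defining the model still lists eye and omits the term.

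Finally, site sizes are not given. Unequal sites would shift the third decimals of the verdict bands but not the SE ratio.

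**Conclusion.** The concern holds as a conditional statement. Sections 10.7 (T3) and 10.8 specify a model that leaves the shared within-subject change out of the error term and does not define the eye effect. With eye nested and rho above 0, the SE is too small by about sqrt(1 + rho), and by more when k is below 0.5. For rho 0.5 to 0.9, a one-sided 5% T3 test runs at about 9 to 13% for k of 1 or more and 11 to 17% at k = 0. With eye crossed, the direction depends on k. The sizes rest on assumed rho and k and on subject-level SDs. The practical consequence is a misstated T3 interval and an unreliable 10.8 test; a changed T3 verdict is unlikely unless the estimate falls near the margin. This should be corrected before analysis.

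**What to change.** In 10.7 (T3), add a random subject-by-part effect. In 10.8, add a random subject-by-treatment effect. In both, state that eye is nested in subject, use Kenward-Roger or Satterthwaite degrees of freedom, and say whether each 95% confidence limit is one- or two-sided.

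Averaging the two eyes and analysing one paired difference per subject gives the same result when both eyes are complete and there is no eye-level covariate. Baseline myopia is allowed as a covariate and can differ between eyes, so the mixed model is the safer wording.

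The cost is one or two lines of SAP text and no change in sample size. Against the nested form, the reported SE rises by a factor of 1.24 to 1.41 (1.29 to 1.52 at k = 0.25, up to 1.69 at k = 0). Against the crossed form, it falls when k exceeds 2. T3 SERE power at a true difference of 0.00 D, with SE 0.0531 D and 42 df, is 99.86% for a one-sided 5% limit and 99.59% for a two-sided 95% interval, both above the planned 99%. Section 10.8 would lose some power compared with the nested form; the plan gives no SD for it, so the loss cannot be stated.

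### The non-inferiority sentences in 10.7 join the SERE and axial length criteria with 'or', and the plan never says that both co-primary endpoints must pass or how a split result is reported

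*Combined protocol and SAP*

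**What the plan says.** Section 3.3 states two primary hypotheses, one for SERE and one for axial length (AL). The first begins "The mean myopic progression (Δ SERE) after cessation of MiSight wear will be noninferior to" the control rate from MIST-401 Part 1, and the second has the same form for AL. The margins follow in one line: "A non-inferiority margin of 0.25D or 0.1mm will be used for SERE and AL respectively".

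Section 10.1 tabulates four tests (two endpoints in each of T3 and T6). Each has its own SD, margin and power, and each is run at one-sided 5%.

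Section 10.3 sets the error control: "The overall type I error rate will be preserved at 5" per cent, and "The co-primary hypotheses will be simultaneously evaluated using α =0.05".

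Section 10.7 holds the decision rule, worded identically for T3 and T6. It opens "Statistical non-inferiority will be concluded if the 95% confidence limit of the mean difference" and sets the condition that this limit "is greater than -0.25D/year for spherical equivalent refractive error or less than +0.1mm/year for axial length". It does not say whether the 95% limit is one-sided or the end of a two-sided interval.

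Section 10.8 uses the same construction for the secondary comparison: "is greater than 0 for spherical equivalent refractive error or less than 0 for axial length".

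**The concern.** The 10.7 sentence offers one conclusion and two criteria joined by *or*. Testing two co-primary endpoints each at the full 0.05 keeps the error at 5% only if both must succeed. If one success is enough, or if each endpoint supports its own free-standing claim, there are two chances of a false positive in each group and the 5% in 10.3 is not secured.

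The plan is also silent on a split result. Suppose SERE meets its margin and AL does not. The text does not settle whether the group is non-inferior, not non-inferior, or non-inferior on one outcome only. That choice would then be made with the data in view, on the main conclusion of an open-label study.

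**Working it through.** **Inputs from 10.1.** n = 46 (T3, paired) and 44 (T6, compared with the 46 T3 subjects). SD for SERE is 0.36 D (T3) and 0.20 D (T6); SD for AL is 0.10 mm in both. Margins are 0.25 D and 0.1 mm, the expected difference is 0, and alpha is one-sided 5%. I take each tabulated SD as the SD of paired differences (T3) or the common between-subject SD (T6).

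**Step 1: reproduce the stated power.** Power = P(noncentral t > critical t), with noncentrality = margin / standard error. The standard error is SD/√46 for T3 (45 df) and SD × √(1/44 + 1/46) for T6 (88 df). One-sided 5% critical values are 1.679 and 1.662.

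| Test | Standard error | Noncentrality | Power | Plan |
|---|---|---|---|---|
| T3 SERE | 0.0531 | 4.71 | 99.86% | 100% |
| T6 SERE | 0.0422 | 5.93 | >99.99% | 100% |
| T3 AL | 0.0147 | 6.78 | >99.99% | 100% |
| T6 AL | 0.0211 | 4.74 | 99.89% | 99% |

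These agree with the plan to within a percentage point and with its text of at least 99%.

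**Step 2: error with both endpoints at their margins.** P(at least one passes) = 2α − P(both pass). This is the false-positive rate of the literal rule, and equally the chance of at least one false claim if SERE and AL are claimed separately. P(both pass) comes from a bivariate normal. The documents do not give the correlation r of the two test statistics (oriented so that passing points the same way for both), so a range is shown.

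| r | One-sided 0.05 | One-sided 0.025 |
|---|---|---|
| 0 | 0.10 − 0.0025 = 9.75% | 0.05 − 0.0006 = 4.94% |
| 0.5 | 0.10 − 0.0122 = 8.78% | 0.05 − 0.0046 = 4.54% |
| 0.7 | 0.10 − 0.0196 = 8.04% | 0.05 − 0.0083 = 4.17% |
| 0.9 | 0.10 − 0.0319 = 6.81% | 0.05 − 0.0148 = 3.52% |

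The right-hand column applies if the 10.7 limit is the end of a two-sided 95% interval.

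**Step 3: one endpoint at its margin, literal reading only.** With AL at +0.1 mm/year and no SERE difference, the literal rule passes the group whenever SERE passes. By Step 1 that is at least 99.86% of the time in T3 and over 99.99% in T6. At one-sided 0.025 the T3 figure is still 99.59%.

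**Step 4: require both.** A false conclusion then needs a test of a true null to reject, so the error is at most 5% per group whatever the correlation. Joint power is at least 1 minus the sum of the misses:

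- T3: 1 − (0.00138 + <0.00001) ≈ 99.86%
- T6: 1 − (0.00001 + 0.00110) ≈ 99.89%

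Both exceed 99.8%.

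**The case against.** A reader might infer that the plan adopts an either-endpoint rule. The documents do not show that.

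- Section 3.3 uses the same *or* with an explicit *respectively* to list one margin per endpoint. The covariate list in 10.7 likewise uses *or* for whichever endpoint is being modelled.
- The 10.7 sentence speaks of one confidence limit, and a single limit is in dioptres or in millimetres, never both. It can be read as applied once per model.
- The two hypotheses are stated and powered separately, and co-primary testing at an unadjusted 0.05 with 5% overall error fits a both-required rule better than an either-or rule.

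This stands, and it limits the claim: the wording is ambiguous and the rule incomplete. It also means that the 99.86% in Step 3 is conditional. If each endpoint has its own conclusion, SERE passes correctly in that scenario and AL will usually fail. The scenario is an extreme one too, since 10.2 itself notes that myopia progression is associated with axial growth. The 6.8% to 9.8% likewise depends on a one-sided 95% limit, which 10.1 supports but 10.7 does not state.

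The objection does not close the gap. The per-endpoint reading yields two verdicts per group and no rule for combining them, and at one-sided 5% two stand-alone claims carry the same 6.8% to 9.8%. No section says that both must pass.

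A reader might also extend the argument to 10.8. It does not carry over, because the co-primary statement in 10.3 does not cover the secondary hypotheses.

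**Conclusion.** The concern holds as an ambiguous and incomplete decision rule for the primary analysis. At the tabulated one-sided 5%, neither the literal reading nor two separate claims delivers the 5% in 10.3: the rate per group is 6.8% to 9.8% with both endpoints at their margins and an assumed correlation of 0.9 to 0. If the limit comes from a two-sided 95% interval, the rate is at most 4.9% for non-negative correlation and the excess disappears, but the missing rule for a split result remains. The near-certain pass with AL at its margin and SERE unchanged belongs to the literal reading alone and should not be quoted as a property of the plan.

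These figures rest on the SDs in 10.1 and on t and normal approximations to the planned mixed models. They concern the endpoint rule within a group; how T3 and T6 combine is a separate matter.

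**What to change.** In both decision sentences of 10.7, state that non-inferiority in a group is concluded only if the SERE limit is above -0.25 D/year **and** the AL limit is below +0.1 mm/year. Add that both endpoint results are reported in every case and that a split result is not declared non-inferior overall. Say in the same place whether the 95% limit is one-sided, as the alpha in 10.1 implies.

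In 10.8, name the SERE and AL claims separately. A joint rule is not needed there.

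The cost is a few words in 10.7 and 10.8, agreed before the data are analysed. Alpha and sample size stay as they are.

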8 8.1 8.2 8.3 8.4 8.5	ADVERSE EVENTS Adverse Event Categorization Adverse Event Reporting Adverse Event Documentation Adverse Event Follow-up Study Completion	32 34 34 34 35 35

9 9.1 9.2 9.3	DATA MANAGEMENT Electronic Case Report Forms/Data Collection Data Quality Assurance Data Entry and Storage	36 36 36 36
10 10.1 10.2 10.3 10.4 10.5 10.6 10.7 10.8 10.9 10.10 10.11	SAMPLE SIZE AND STATISTICAL METHODS Sample Size Rationale Primary End-points Statistical Considerations Analysis Population Descriptive Statistics Data Pooling Primary Statistical Analysis Secondary Statistical Analysis Tertiary Statistical Analysis Interim Analysis	36 36 37 38 38 38 38 38 39 39 39
11 11.1 11.2 11.3 11.4 11.5 11.6 11.7 11.8 11.9	GENERAL STUDY MANAGEMENT Relevant Standards Ethics Review Protocol Deviations Premature Termination of the Study Source Documentation Monitoring Audits Records Retention Confidentiality and Publication	40 40 40 40 40 40 41 41 41 42 42
12	REFERENCES	43
APPE	NDIX A PROCEDURES, EQUIPMENT AND GRADING SCALES	44
APPE	NDIX B ADVERSE EVENT FORMS	62

MiSight[®] Lens Wear Cessation Study

MIST-402

PERSONNEL AND FACILITIES

SPONSOR:

CooperVision Inc. [name]

CLINICAL PROJECT LEADER:

Tel: Email

INVESTIGATORS:

(listed separately)

STUDY LOCATION:

UK, Portugal, Singapore and Canada

CLINICAL RESEARCH ORGANISATION:

Visioncare Research Ltd

MEDICAL MONITOR:

STATISTICIAN:

DATA MANAGER:

Tel: Email:

MiSight[®] Lens Wear Cessation Study

MIST-402

SYNOPSIS

STUDY OBJECTIVES: To	o quantify the effect of ceasing I	MiSight treatment after 3 or 6 years' use.
----------------------	------------------------------------	--

- **STUDY DESIGN:** This will be a bilateral, open label, dispensing study with approximately 90 MiSight subjects refit to Proclear 1-day lens for 1 year.
- **RANDOMISATION:** All subjects will be refit to Proclear 1 Day. As such, no randomization will take place.

MASKING: There will be no masking for this study.

TEST PRODUCTS: Lenses to be worn are shown below:

Brand	Proclear 1 Day
Manufacturer	CooperVision
Material/ water content	omafilcon A / 62%
Design	Single vision
Base curve (mm)	8.70
Diameter (mm)	14.2
Sphere powers (D)	-0.25 to -8.00 (0.50D steps after -6.00D)

LENS CARE PRODUCTS: These are daily disposable lenses and, therefore, contact lens cleaning, soaking and disinfecting products should not be required

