1 INTRODUCTION

The three-year pivotal study (MIST-401; CVI08008) noted a significant reduction in myopic progression and axial growth with MiSight in comparison with a single vision control.¹

Myopia progression studies with atropine eyedrop treatment have noted what appeared to be an acceleration of progression when the treatment with atropine was ceased. During the 12-months after cessation, with 1% concentration the average rate of myopia progression was greater than that shown by a control group.² Subsequent studies by the same group studied both the efficacy and post study acceleration following treatment and then cessation of lower concentrations of atropine (0.01%, 0.1%, 0.5%). These concentrations showed a dose dependent post-treatment acceleration compared to the 1% concentration.³

There is only one published study involving soft contact lenses with positive spherical aberration that has investigated myopia progression following cessation of treatment. This study found no evidence of a rebound effect after ceasing treatment.⁴

The purpose of this study will be to investigate the effect of ceasing treatment with MiSight contact lenses.

In MIST-401, subjects were randomly assigned to one of two groups: the test group wore MiSight contact lenses while the control group wore Proclear 1 Day lenses. After completion of this 3-year pivotal study ("Part 1"), all subjects were offered the opportunity to enrol for an additional three-year study, all wearing MiSight lenses (MIST-401 Part 2).

Subjects who have completed the MIST-401 MiSight study (Part 1 and Part 2) will be invited to enrol on this 1-year follow-on study (MIST-402). Thus, subjects entering the study will have worn MiSight lenses for either 3 or 6 years.

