6 TREATMENT

6.1 Study Product Formulations

The test lenses will be shipped in blister packs containing a buffered saline packaging solution. The labelling of lenses and packaging will be the standard packaging which will indicate lens power, base curve, diameter, lot number and expiration date.

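### Does the undefined test-minus-control difference in Section 10.8 reverse the secondary hypothesis?

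*Combined protocol and SAP*

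**What the plan says.** Section 3.4 gives the direction of the secondary hypotheses: for both spherical equivalent refractive error (SERE) and axial length (AL), mean progression "after cessation of MiSight wear will be greater than the mean annual myopic progression" of the previous three MiSight years (MIST-401 Part 2). Section 3.2 likewise expects a slightly higher rate in ordinary lenses.

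Section 10.8 sets up the matching within-subject comparison: "The myopic progression after cessation of MiSight wear will be compared to the mean annual myopic progression for previous" three years on MiSight, in a mixed model with treatment as a fixed effect. It then concludes a difference, at the 95% level, on this condition: "confidence limit of the mean (test-control) difference is greater than 0 for spherical equivalent refractive error or less than 0 for axial length". Section 10.8 does not attach test or control to either period.

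The labels occur elsewhere:

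- Section 1, on MIST-401: "the test group wore MiSight contact lenses while the control group wore Proclear 1 Day lenses".
- Section 3.2 refers to the rate "found in the Control group (Proclear 1-Day) in the 3-year MIST-401" study, Part 1.
- Section 10.1 identifies T6 as the test group of Part 1 and T3 as its control group.
- The Synopsis introduces the Proclear 1 Day details with "TEST PRODUCTS: Lenses to be worn are shown below", and Section 6.1 says "The test lenses will be shipped in blister packs".

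Section 10.7 uses no such labels. It asks whether the limit for the rate "after cessation compared to the T3 Baseline rate is greater than -0.25D/year for spherical equivalent refractive error", or below +0.1 mm/year for axial length.

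**The concern.** In this study every subject is refitted to Proclear 1 Day, and the Synopsis and Section 6.1 call that lens the test product. Section 10.7 and the opening sentence of Section 10.8 both put the period after cessation first and the reference second. A reader coming straight from Section 10.7 could therefore take test minus control as after cessation minus MiSight. On that reading the printed signs demand slower progression after cessation on both endpoints, the reverse of Section 3.4. A real acceleration would then almost never meet the rule, and a real slowing would meet it.

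The formal conclusions on both secondary endpoints would be affected. The sentence also leaves open whether the 95% limit is one-sided or two-sided.

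**Working it through.** **Scale.** The limits in Section 10.7 (-0.25 D/year and +0.1 mm/year) imply signed change: more myopia is negative for SERE and positive for AL. Section 10.8 prints opposite signs for the two endpoints, which also makes sense only on a signed scale. The phrase in Section 10.2 about the magnitude of change does not alter this, because on an unsigned scale neither labelling would fit both signs.

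**Sign check.** Let D = annual change after cessation minus mean annual change in Part 2. Section 3.4 predicts D < 0 for SERE and D > 0 for AL.

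| Test is | Test minus control | SERE rule requires | AL rule requires | Agrees with 3.4 |
|---|---|---|---|---|
| MiSight (Part 2) | -D | D < 0 | D > 0 | both endpoints |
| Proclear 1 Day (after cessation) | D | D > 0 | D < 0 | neither endpoint |

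**Which labelling the documents support.** A difference of test minus control needs both labels. Section 1 supplies both for the same two products, and Sections 3.2 and 10.1 repeat them. The Synopsis and Section 6.1 use test for the only lens dispensed and name no control beside it. No section calls MiSight the control. The models point the same way. For T3, Section 10.7 compares Proclear wear with Proclear wear and uses a factor called part. Section 10.8 compares MiSight with Proclear 1 Day and uses a factor called treatment, whose levels are the two products labelled test and control in MIST-401.

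**Which limit.** For the interval to exclude 0, greater than 0 must refer to the lower limit (SERE) and less than 0 to the upper limit (AL).

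**The plan's own figures.** Section 10.1 gives power for the primary tests only. With a true difference of 0 and one-sided 5%, power = Φ(margin/SE - 1.645):

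- SERE, T3: SE = 0.36/√46 = 0.0531; Φ(4.71 - 1.645) = 0.999 (stated 100%).
- SERE, T6: SE = 0.20·√(1/44 + 1/46) = 0.0422; Φ(5.93 - 1.645) > 0.999 (stated 100%).
- AL, T3: SE = 0.10/√46 = 0.0147; Φ(6.78 - 1.645) = 1.000 (stated 100%).
- AL, T6: SE = 0.10·√(1/44 + 1/46) = 0.0211; Φ(4.74 - 1.645) = 0.999 (stated 99%).

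These reproduce, and none depends on the labels in Section 10.8.

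**What the label would move.** The documents give no effect size or SD for the secondary contrast. Assume 90 subjects (44 + 46), the T3 paired SDs from Section 10.1 (0.36 D, 0.10 mm; given there for a different contrast), and true accelerations of 0.10 D/year and 0.05 mm/year.

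- SERE: SE = 0.36/√90 = 0.0379; 0.10/SE = 2.635. MiSight as test: Φ(2.635 - 1.645) = 0.84. Proclear as test: Φ(-2.635 - 1.645) = 0.000009.
- AL: SE = 0.10/√90 = 0.0105; 0.05/SE = 4.743. MiSight as test: Φ(4.743 - 1.645) = 0.999. Proclear as test: below 0.000001.

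**What sidedness would move.** With MiSight as test and the limit of a two-sided 95% interval, the SERE figure becomes Φ(2.635 - 1.960) = 0.75 and the AL figure 0.997. For SDs from 0.20 to 0.50 D at 0.10 D/year, the SERE probability runs from 0.999 to 0.60 one-sided and from 0.997 to 0.475 two-sided.

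**The case for a change.** The strongest case for a change is that a pre-specified rule should stand on its own text. To prefer the labelling that makes the signs work is to infer the rule from the result it is meant to deliver. This protocol's own use of test points to Proclear 1 Day, Section 10.7 runs in the opposite direction, and in an open-label study an outsider could not show afterwards that the direction was fixed in advance. One sentence would settle it.

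Part of this stands. The label is not written in Section 10.8, the subtraction does run opposite to Section 10.7, and the one-sided 5% entry in Section 10.1 covers only the primary tests. The charge of circularity does not stand. The MIST-401 pairing is stated in Section 1 independently of the signs, and the direction is fixed by Section 3.4, not by the data. The feared outcome is also narrower than two opposite conclusions: with data showing acceleration, the reversed rule would fail to conclude a difference, but it would not conclude slowing. The estimate and its interval would still show the direction. The gap between 0.84 and nearly zero is what reversing any directional rule produces, so it adds no evidence about which labelling is meant.

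**Conclusion.** The concern does not call for a change. Read with the only explicit test and control pairing in the documents, Section 10.8 tests Section 3.4 in the right direction on both endpoints. The contradiction appears only under a labelling that requires MiSight to be the control, which no section says. Reversing the subtraction changes only the sign of the secondary estimate, and the primary non-inferiority analyses and their power are untouched.

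Two details are left to the analyst. The label can be read from Sections 1, 3.2 and 10.1. Sidedness is less settled, although Section 10.7 uses the same 95% limit wording for tests that Section 10.1 specifies as one-sided 5%, and the hypotheses in Section 3.4 are directional. Under the assumptions above, the choice is worth about 0.09 in the SERE probability at 0.10 D/year (0.84 against 0.75) and almost nothing for AL at 0.05 mm/year. The sign argument rests on the signed scale implied by Section 10.7 and on no assumed figure. The probabilities rest on assumed effects, a borrowed SD, full retention of 90 subjects, and a simple paired comparison in place of the two-eye mixed model.
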